### **3.3.3 Other outcomes**

To assess the safety of YZASG compared to placebo in subjects with aMCI, the investigators will record the incidence and severity of treatment-emergent adverse events (TEAEs), and clinically important changes in safety assessment results (including vital signs, weight, clinical laboratory tests, physical and neurological exams, ECGs, and MRIs).

## **4. Statistical considerations**

### **4.1 Sample size**

Using pre-intervention and post-intervention scores obtained from Miao *et al.*, 33 patients are needed for inclusion in the treatment group to achieve a statistical power of 90%. Allowing for a maximum dropout rate of 20%, the number of subjects in the treatment group has been set to 40 patients with aMCI. With the allocation ratio of 1:1, 40 subjects will be randomized to the placebo group.

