intracranial lesion, a disturbance of cerebral spinal fluid circulation (e.g., normal pressure hydrocephalus), and/or a significant history of head trauma or brain surgery; (12) has signs of major cerebrovascular disease, with score of modified Hachinski Ischemia Score (mHIS) at more than 4, or as verified by medical history and/or brain MRI or CT; (13) has severe visual or hearing impairments that cannot cooperate with examinations; (14) has severe digestive system diseases; (15) has received antibiotics within 60 days prior to screening.

Handling of withdrawal and dropout: (1) Voluntarily withdrawal, (2) loss of follow-up, (3) poor compliance and presence of severe adverse effects, (4) revealing and uncovering blind in urgency, (5) misdiagnosis, (6) using forbidden drugs or treatments in the course of the trial, (7) taking no medication during the trial, (8) no evaluable records after medication. Reasons for withdrawing participants will be recorded in CRFs, and the last data will be included in data analysis.

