### **3.3 Outcomes**

#### **3.3.1 Primary outcome**

Cognitive decline is measured using the Chinese version of the Alzheimer Disease Assessment Scale-Cognitive subscale (ADAS-cog11). The total possible score is 70. A score increase indicates greater severity of impairment. The specific hypothesis is that the change from baseline to endpoint will be significantly less than that for placebo.

The ADAS-cog will be assessed at baseline (before intervention), at 16 weeks (the end of intervention) and 6, 12, and 18 months after intervention.

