### **4.2 Statistic analysis**

Analysis will be conducted by a statistician of the National Clinical Trial Center of Chinese Medicine (Chengdu, China), who will be blinded to the whole trial and using SAS 9.2 software (Cary, NC, USA) and SPSS 19.0 software (IBM, NY, USA).

Unless otherwise specified, all mechanism, efficacy and safety analyses will be strictly conducted according to the intention-to-treat (ITT) principle and the full analysis set (FAS) population, the per-protocol set (PPS) population and the safety set (SS) population. Missing values will be replaced by the last observation carried forward (LOCF) method. ADAS-cog (including its monomial item) changes from baseline and the secondary outcomes will be assessed using an analysis of covariance with treatment groups as factors and baseline values as covariates. Standardized mean

differences will be used to express effect sizes in SD. The baseline homogeneity of the baseline characteristics between the two groups will be analyzed with Fisher's exact test, or  $\chi^2$  test for categorical measures and with the *t* test or Wilcoxon rank-sum test for continuous measures. The statistical significance is defined as a one-sided P-value of <0.05 and 95% confidence interval.

For the gut microbiome analysis, sequenced data will be interpreted using the bioinformatics tools programmed in the Ion Reporter software. QIIME algorithms will determine the bacterial diversity within a sample ( $\alpha$  diversity) and among all the samples ( $\beta$  diversity). Additionally, multivariate data analysis with principal component analysis on the diversity indexes and comparisons of genus and species level data will be performed to reveal differences in the microbial composition between individuals with normal cognition and ones with aMCI. The Benjamini–Hochberg false discovery rate adjustment will be used to account for the number of taxa tested in each comparison.

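### Section 4.1: 40 per arm less the stated maximum 20% dropout leaves 32 completers, one short of the 33 said to be needed for 90% power

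*Combined protocol and SAP*

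**What the plan says.** Section 4.1 (Sample size) takes scores from a cited study and concludes that "33 patients are needed for inclusion in the treatment group to achieve a statistical power of 90" per cent. It then inflates for attrition: "Allowing for a maximum dropout rate of 20%, the number of subjects in the treatment group has been set to 40 patients with aMCI". The second arm follows from the first: "With the allocation ratio of 1:1, 40 subjects will be randomized to the placebo group". Section 4.1 gives no effect size, SD, significance level, test or time point, and does not say which analysis set the 33 refers to.

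Three other places bear on the point:

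- Section 4.2 (Statistic analysis) sets the level: "The statistical significance is defined as a one-sided P-value of <0.05 and 95% confidence interval". It names full-analysis, per-protocol and safety sets, and handles missing data as follows: "Missing values will be replaced by the last observation carried forward (LOCF) method".
- Section 3.1, on withdrawals and dropouts, says that "the last data will be included in data analysis".
- Section 3.3.1 gives the timing of the primary outcome: "The ADAS-cog will be assessed at baseline (before intervention), at 16 weeks (the end of intervention"), followed by visits at 6, 12 and 18 months after intervention.

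**The concern.** A dropout allowance is meant to ensure that, at the worst attrition planned for, the number still evaluable is at least the number required for the stated power. Here the inflated size, reduced by the stated maximum, does not return the starting figure. For completers, the 20% allowance and the 90% power cannot both be true with 40 per arm. What is at stake is the accuracy of a published design figure, and with it the margin that anyone monitoring attrition would think they have. The trial's validity is not in question.

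**Working it through.** **Inputs.** From section 4.1: 33 required in the treatment group, 90% power, maximum dropout 20%, 40 planned per arm (80 in total). From section 4.2: one-sided 0.05. The effect and SD are not given, so the 33 itself cannot be reproduced.

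**Step 1: reproduce the plan's 40.** Multiplying by one plus the dropout rate: 33 × 1.20 = 39.6, rounded up to 40. This matches the plan exactly.

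**Step 2: apply the stated dropout to that 40.** 40 × (1 − 0.20) = 32 completers per arm, one fewer than 33.

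**Step 3: the size that would deliver the allowance.** n/(1 − dropout) = 33/0.80 = 41.25, rounded up to 42. Check: 41 × 0.80 = 32.8 (short); 42 × 0.80 = 33.6 (sufficient). The full allowance needs 42 per arm, 84 in total against the planned 80.

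**Step 4: the dropout that 40 per arm can absorb.** 40 − 33 = 7 dropouts; 7/40 = 17.5%.

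**Step 5: power at 32 per arm.** Assumption: 33 per arm gives exactly 90% for a two-sample t comparison at one-sided 0.05. Power is the probability that a noncentral t with 2n − 2 degrees of freedom and noncentrality d√(n/2) exceeds the 95th percentile of the central t.

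| Quantity | Value |
|---|---|
| d giving 90% at 33 per arm | 0.728 |
| Power at 32 per arm, d = 0.728 | 89.2% |
| d giving 90% at 32 per arm | 0.740 |
| Power at 32 per arm if 33 was itself rounded up (d between 0.728 and 0.740) | 89.2% to just under 90% |
| Power at 32 per arm if sizing was two-sided 0.05 (d = 0.810) | 89.1% |

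The loss is about one point of power or less, on either sidedness.

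**Step 6: what carrying observations forward would do.** Same assumed effect, d = 0.728, with all 40 per arm analysed.

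- No dilution of the effect: power 94.3%.
- Most diluted case considered: all 8 dropouts per arm leave before the first post-baseline ADAS-cog listed in section 3.3.1 (week 16) and carry baseline forward as zero change, with flat placebo and unit SD of change. Mean difference 0.8 × 0.728 = 0.583. Variances: 0.8 + 0.16 × 0.728² = 0.885 on active, 0.8 on placebo. Diluted d = 0.583/√[(0.885 + 0.8)/2] = 0.635. Power 87.9% by noncentral t, 88.7% by simulation (400,000 trials with exactly 8 zeros per arm).
- By the same noncentral t method, power is 90.8% with 5 such leavers per arm and 89.9% with 6.

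Analysing all 40 can therefore put power on either side of 90%.

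**The case against.** The strongest reply is that the plan never calls the 33 completers. Section 4.2 puts efficacy on an intention-to-treat footing with last observation carried forward, and section 3.1 keeps withdrawn participants' last data, so the full analysis set may retain up to 40 per arm, well above 33. That is a fair limit on the claim, and the point is confined to completers for that reason. It does not rescue the sentence: inflating 33 for dropout makes sense only if 33 are meant to remain evaluable, and step 6 shows that carrying values forward does not guarantee 90%.

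Four narrower objections:

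- **Timing.** Section 4.1 does not say whether the 20% applies by week 16 or over the whole follow-up. If at least one of the 8 leavers per arm goes after week 16, 33 are still present at that visit. This is true, but the sum 40 × 0.80 = 32 is unchanged at whatever visit the maximum is reached.
- **Adjusted analysis.** Section 4.2 specifies analysis of covariance. If the 33 came from an unadjusted calculation and baseline correlated 0.2 or 0.3 with change (illustrative values), power at 32 would be 90.2% or 91.5%. So the power figures hold on the sizing basis assumed here and are not a forecast for the planned model. Since section 4.1 states 33 as the number needed, 32 falls below 90% on the plan's own basis.
- **The 88% case is extreme.** It requires every leaver to go before any post-baseline primary measurement. Section 3.3.2 also says that all questionnaires are assessed at week 8; if that includes the ADAS-cog, week-8 values could be carried forward instead of baseline. The figure is a conditional illustration, and the finding does not depend on it.
- **Materiality.** One patient per arm, at maximum dropout only, is negligible for the trial's conclusion. That is accepted and is why the point is rated minor.

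**Conclusion.** The concern holds as a minor arithmetic error. On section 4.1's own numbers, 40 per arm does not cover a 20% loss while keeping 33: it leaves 32, and the largest loss it covers is 17.5%. The full allowance would need 42 per arm. This part needs no assumption beyond reading the 33 as the number who must remain evaluable, and confidence in it is high.

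The power statement (89.2%, or up to just under 90% if 33 was rounded up) is less firm. It rests on the assumed two-sample comparison at one-sided 0.05 with exactly 90% at 33 per arm, because section 4.1 gives no sizing inputs. Whether 33 is itself right cannot be checked from the documents.

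**What to change.** Keep 80 participants and restate the sentence in section 4.1, for example: 40 per arm retains 33 completers per arm up to 17.5% dropout (7 of 40); at 20% dropout 32 per arm complete, and power is slightly below 90%. The exact power at 32 should be computed from the sponsor's own sizing inputs.

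The cost is rewording one sentence, with no extra patients and no design change. The only downside is a slightly less favourable stated figure.

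Separately, as a question to the sponsor and not as an error: state the effect, SD and time point behind the 33, and confirm that it refers to the between-arm comparison at the one-sided 0.05 level of section 4.2.

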### **4.2 Statistic analysis**

Analysis will be conducted by a statistician of the National Clinical Trial Center of Chinese Medicine (Chengdu, China), who will be blinded to the whole trial and using SAS 9.2 software (Cary, NC, USA) and SPSS 19.0 software (IBM, NY, USA).

Unless otherwise specified, all mechanism, efficacy and safety analyses will be strictly conducted according to the intention-to-treat (ITT) principle and the full analysis set (FAS) population, the per-protocol set (PPS) population and the safety set (SS) population. Missing values will be replaced by the last observation carried forward (LOCF) method. ADAS-cog (including its monomial item) changes from baseline and the secondary outcomes will be assessed using an analysis of covariance with treatment groups as factors and baseline values as covariates. Standardized mean

differences will be used to express effect sizes in SD. The baseline homogeneity of the baseline characteristics between the two groups will be analyzed with Fisher's exact test, or  $\chi^2$  test for categorical measures and with the *t* test or Wilcoxon rank-sum test for continuous measures. The statistical significance is defined as a one-sided P-value of <0.05 and 95% confidence interval.

For the gut microbiome analysis, sequenced data will be interpreted using the bioinformatics tools programmed in the Ion Reporter software. QIIME algorithms will determine the bacterial diversity within a sample ( $\alpha$  diversity) and among all the samples ( $\beta$  diversity). Additionally, multivariate data analysis with principal component analysis on the diversity indexes and comparisons of genus and species level data will be performed to reveal differences in the microbial composition between individuals with normal cognition and ones with aMCI. The Benjamini–Hochberg false discovery rate adjustment will be used to account for the number of taxa tested in each comparison.

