**April 14, 2018**

# **Efficacy Study of Yi-Zhi-An-Shen Granules for Older Adults with Amnestic Mild Cognitive Impairment**

## **Study Protocol with SAP**

### **1. Objectives**

The primary objective of this study is to evaluate the efficacy and safety of Yi-Zhi-An-Shen Granules (YZASG) in optimizing cognitive performance over time in elderly individuals with amnestic mild cognitive impairment (aMCI). Secondly, the investigators intend to assess whether YZASG can improve sleep quality among aMCI patients. Finally, participants' fecal genomic DNA will be extracted to analyze the gut microbial differences between individuals with aMCI and ones with normal cognition.

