### **3. Methods**

#### **3.1 Participants**

The investigators anticipate recruiting 80 participants from Teaching hospital of Chengdu University of Traditional Chinese Medicine, community, and nursing homes. All patients will undergo standard medical examination and neuropsychological testing to ensure correct diagnosis of aMCI.

The inclusion criteria are (1) subject has assigned informed consent to participate in the study and continues to give willing consent for participation; (2) age from 60 to 85 years with a diagnosis of aMCI; (3) educational level of at least 6 years; (4) availability of a "study partner" who can assist in completing rating scales for the duration of the study; (5) cognitive complaints reported by the subject and confirmed by the "study partner"; (6) clinical Dementia Rating (CDR) global score of 0.5, and memory item score of 0.5; (7) mini-mental state examination (MMSE) score of 24-30; (8) Diagnostic and Statistical Manual of Mental Disorders, Version 5 (DSM-V) criteria of dementia not fulfilled

The exclusion criteria are as follows: (1) has been previously enrolled in this study and received the investigational product; (2) has received an investigational product within 30 days prior to screening; (3) has received disease-modifying therapy; (4) has a known allergy to the study drug or any of its constituents; (5) has a history of alcohol abuse or alcohol dependency in the 3 years prior to study entry, or is an alcoholic or drug addict, as determined by the investigator; (6) has ongoing clinically significant (as judged by the investigator), metabolic or any other disease that could currently cause impaired memory (e.g., untreated thyroid disease, vitamin or other nutritional deficiencies, chronic kidney, or liver disease); (7) memory impairment that can be attributed to a disease or condition other than an early phase neurodegenerative syndrome; (8) has a parkinsonian movement disorder; (9) use of psychoactive medications that would affect the subject's ability to reliably perform neurocognitive testing or create uncertainty in distinguishing between the effects of the psychoactive medication and the subject's underlying cognitive impairment (e.g., benzodiazepines, sedatives, antipsychotics); (10) with history of major recurrent depressive disorder (DSM-V) within the last 5 years prior to screening; (11) has a brain tumor or other

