These clinical tests will be administrated by a trained, certified clinician or rater experienced in the assessment of patients with cognitive deficits. And the rater who will conduct the CDR for a patient cannot complete any other rating scales for the same patient, and will be blinded to the results of all other neuropsychological scales. All the questionnaires will be assessed at baseline (before intervention), at 8 and 16 weeks (during intervention) and 6, 12, and 18 months after intervention.

- Fecal genomic DNA will be extracted from frozen stools using QIAamp DNA mini stool kit (Qiagen, Hiden, Germany), obtained from the patients with aMCI and 15-20 participants with normal cognition at baseline. After PCR amplification, DNA fragments will be sequenced on an Illumina HiSeq 2500 instrument and an Illumina HiSeq X instrument for 16SrDNA and metagenomics analyses respectively at Biomarker Technologies Co, Ltd (Beijing, China) to analyze the differences in gut microbiome between patients with aMCI and individuals with normal cognition.

When it is available, the investigators will also assess the change in gut microbiome between the treatment group and the placebo group after the intervention of YZASG in the same way.

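### LOCF is the only planned missing-data method for ADAS-cog; at the 6-, 12- and 18-month visits it can favour the arm with more or earlier dropout, or prolong a faded effect

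*Combined protocol and SAP*

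**What the plan says.** All references are to the combined protocol and SAP.

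- **Section 4.2:** "Missing values will be replaced by the last observation carried forward (LOCF) method". ADAS-cog change and the secondary outcomes are analysed by ANCOVA with treatment and baseline. The section names ITT, FAS, PPS and safety sets. These are analysis populations, not missing-data methods. No missing-data sensitivity analysis appears.
- **Section 3.1 (withdrawal and dropout)** agrees with LOCF: "Reasons for withdrawing participants will be recorded in CRFs, and the last data will be included in data analysis". It lists "no evaluable records after medication" as a withdrawal category but does not say whether such participants stay in the FAS.
- **Section 3.3.1** describes ADAS-cog as a measure of cognitive decline on which higher is worse. After baseline it is taken "at 16 weeks (the end of intervention) and 6, 12, and 18 months after intervention". The hypothesis reads: "The specific hypothesis is that the change from baseline to endpoint will be significantly less than that for placebo". The endpoint visit is not named.
- **Section 1** sets the aim as "optimizing cognitive performance over time in elderly individuals".
- **Section 4.1** bases the sample size on scores before and after intervention, which points to week 16 without saying so. It allows for at most 20% dropout.

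**The concern.** LOCF freezes a participant's score at the last visit attended. On a scale chosen to track worsening, that assumes dropouts stop worsening and that any benefit at the end of treatment never fades. Neither is a safe assumption for follow-up that runs 18 months past a 16-week treatment. Two routes to bias follow:

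- **(a) Unequal dropout.** If participants decline, the arm that loses more people, or loses them earlier, has more scores frozen at a better level and looks better.
- **(b) Fading effect.** Even with equal dropout, YZASG participants last seen while an effect was present keep that effect at later visits.

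At stake are the follow-up contrasts, which are what would show whether any benefit lasts. The fill-in rule could create, hide or prolong a benefit there, and nothing planned would reveal it.

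**Working it through.** **Inputs from the documents.** 40 per arm, at most 20% dropout, one-sided 5%, ANCOVA on baseline. The 40 follows from 33 × 1.2 = 39.6, rounded up. Visits in years from baseline: 0; 16/52 = 0.31; then 0.81, 1.31 and 1.81.

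**Assumed, because the documents give none.** Decline of 1-3 points a year. Intercept SD 4, slope SD 2, residual SD 3. Dropouts' last visit spread evenly over the first four visits unless stated.

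**Standard error at 18 months (complete data).** The variance of the score is 4² + (2 × 1.81)² + 3² ≈ 38.1. Baseline variance is 4² + 3² = 25 and the covariance is 16. The variance given baseline is 38.1 − 16²/25 ≈ 27.9, so SD ≈ 5.28 and SE ≈ 5.28 × √(2/40) ≈ 1.18. Rejection is then about Φ(−1.645 + bias/SE). Simulation (6,000-10,000 trials per scenario) agrees closely.

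**Route (a), no true effect.** Bias = decline rate × dropout difference × mean follow-up lost.

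- Mean last visit is (0 + 0.31 + 0.81 + 1.31)/4 = 0.61 years, so 1.81 − 0.61 = 1.20 years are lost.
- 18 months, 20% (YZASG) against 10%: 0.10 × 1.20 × 1 to 3 = 0.12-0.36 points towards YZASG. Rejection is Φ(−1.645 + 0.10) ≈ 6% to Φ(−1.645 + 0.31) ≈ 9%; simulated 6.3-9.3%.
- Split reversed: same size against YZASG; simulated rejection 2.8-4.2%.
- Equal 20% with equal timing: bias nil, rejection about 5%. No decline, 20% against 10%: bias nil, rejection 5.2%.
- 12 months, 20% against 10%: 0.10 × (1.31 + 1.00 + 0.50)/4 × 1 to 3 = 0.07-0.21 points. 6 months: 0.10 × (0.81 + 0.50)/4 × 1 to 3 = 0.03-0.10 points.
- If the FAS leaves out participants with no post-baseline value, the 18-month dropout difference is 15/95 − 7.5/97.5 = 0.081 and 1.00 year is lost. Bias is 0.08-0.24 points, simulated rejection 5.8-7.4%.
- If dropout follows observed worsening (about 20% against 12%), simulated 18-month bias runs from 0.02 points against YZASG to 0.17 towards it, with rejection 4.8-6.8%.

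**Route (b), week-16 effect of 2-3 points, zero by 18 months, equal 20% dropout.** Bias = 0.20 × mean share of the effect frozen × effect.

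| Pattern | Share frozen | Bias at 18 months | Rejection |
|---|---|---|---|
| Gone by the 6-month visit, dropout spread | (0 + 1 + 0 + 0)/4 = 0.25 | 0.10-0.15 | 6-7% |
| Linear fade to 18 months, dropout spread | (0 + 1 + 2/3 + 1/3)/4 = 0.5 | 0.2-0.3 | 7-8.5% |
| Every dropout last seen at week 16 | 1 | 0.4-0.6 | 9-13% |

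**Week 16.**

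- Worst case with no effect (all dropout before week 16, baseline carried forward, 20% against 10%): 0.10 × 0.31 × 1 to 3 = 0.03-0.09 points; rejection 5.4-6.5%.
- True 3-point effect, equal 20% dropout: 3 × 0.80 = 2.4 if all leave before week 16. If dropout is spread, 5% leave before week 16 and the estimate is 3 × 0.95 = 2.85. Simulated power in the first case is 91% with LOCF and 92% with a mixed model.

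**Mixed model.** Under the null and fading scenarios a repeated-measures model with unstructured covariance had simulated bias of at most 0.024 points and rejection of 4.3-5.1%. Dropout in these scenarios meets that model's own assumption, so this does not show robustness to other mechanisms.

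**The case against.** The strongest reply is that the harm lies outside the main test. Section 4.1 suggests the endpoint is week 16, where the false-positive risk is small and power is nearly unchanged, and section 3.3.1 states no separate hypothesis for the later visits. This largely stands, and it is why the point is not fatal. But the endpoint visit is unnamed, section 1 sets the aim as performance over time, and the follow-up visits have little purpose if their contrasts cannot be read.

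Second, the sizes rest on assumed inputs and are modest. That also stands: 0.12-0.36 points is about 0.1-0.3 of a standard error. Both arms receive exercise, health education and nutritional support, so slow decline cannot be excluded, and route (a) vanishes at zero decline.

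Third, a mixed model has assumptions too. True, which is why a delta-adjusted analysis belongs beside it.

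A reader might infer more than the documents support:

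- **That LOCF systematically favours YZASG.** Under (a) the direction depends on which arm loses more or earlier, and section 4.1 gives no split. Only (b) has a fixed direction, and it needs an effect that has faded.
- **That false-positive rates far above 10% are likely.** Under route (a), getting there takes, for example, 30% dropout on YZASG, which exceeds the 20% maximum in section 4.1.
- **That the sections contradict each other on week 8.** Section 3.3.2 says "All the questionnaires will be assessed at baseline (before intervention), at 8 and 16 weeks (during intervention"), but this stands under secondary outcomes, while section 3.3.1 gives ADAS-cog its own schedule. A conflict is possible, not established.

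**Conclusion.** The concern holds for the follow-up visits and should be fixed; it does not show that the main test is invalid. As sole method, LOCF leaves the 6-, 12- and 18-month ADAS-cog contrasts open to distortion in either direction, with no planned check.

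At 18 months, under the stated assumptions, the distortion is roughly 0.1-0.4 points with rejection of 6-9% in most adverse scenarios. It reaches 0.4-0.6 points and 9-13% only if a 2-3 point effect has faded and every dropout was last seen at week 16. Under (a) it grows with length of follow-up. It is nil when dropout and timing are equal and no earlier effect has faded.

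If the endpoint is week 16, the main harm there is a diluted estimate when baseline is carried forward, not a false positive. That LOCF is the only method is certain from the text. The size of its effect is not, because decline rate, SD and per-arm dropout are all assumed.

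**What to change.** In section 4.2:

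1. Name the primary ADAS-cog visit.
2. Make the main analysis of ADAS-cog total, and of the approximately continuous scale scores (MMSE, MoCA, CDR-SB, PSQI, and ADL scores where their distribution allows), a mixed model for repeated measures on all observed data. Outcome: change from baseline. Terms: treatment, visit, treatment-by-visit, baseline, baseline-by-visit. Covariance: unstructured, with a named fallback. Report the contrast at the primary visit and at each follow-up visit.
3. Keep LOCF ANCOVA as a sensitivity analysis, stating whether participants with only a baseline value are included, beside a delta-adjusted (tipping-point) multiple imputation.
4. Analyse CDR global by a categorical or ordinal method without a baseline term. Section 3.1 requires "clinical Dementia Rating (CDR) global score of 0.5, and memory item score of 0.5", so its baseline is constant and the term cannot be estimated.
5. Clarify whether the week-8 assessment includes ADAS-cog, since that sets the model's visits.

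The cost is SAP wording and code in the SAS package already named, with no new visits. The downsides are more model specification and a somewhat wider 18-month confidence interval, because filled-in values no longer count as observed.

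Continuing the already scheduled assessments in consenting participants who stop study product is also desirable. It is a separate change to trial conduct, and this fix does not depend on it.

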#### **3.3.2 Secondary outcome**

Secondary measures includes the MMSE, MoCA (Changsha Version), CDR, PSQI, ADLs, and gut microbiome.

- The MMSE is an 11-question measure that tests five areas of cognitive function (orientation, registration, attention and calculation, recall, and language). The maximum score is 30 and a score below 24 is considered abnormal for dementia screening.
- The MoCA (Changsha Version) will also be used to evaluate general cognitive function, as it contains visuospatial processing and organizational capability which can make up for the shortcoming of the MMSE. The total score for it is 30, with a higher number indicating a more intact cognitive function. Meanwhile, the MoCA has been shown to be a promising tool to detect MCI and early AD.
- The CDR will be used as an assistant evaluation for patients' dementia severity, which scored 0-3, with higher scores indicating more severity. It is a semi-structured interview performed with the patient and caregiver (informant),

characterizing six domains of cognitive and functional performance. The CDR sum of boxes (CDR-SB) scored 0-18, will also be applied to assess patients' cognitive status, with higher scores indicating worse functioning.

- The Pittsburgh Sleep Quality Index (PSQI) will be used to assess participants' comprehensive quality of sleep, which involves sleep quality, sleep duration, sleep efficiency, sleep disorders, daytime dysfunction, sleeping aids, etc. The total score for it is 21, with a higher score indicating a worse sleep quality.
- ADLs will be assessed including basic activities of daily living (BADL) and instrumental activities of daily living (IADL). An individual's BADL will be evaluated mainly by the subjects' performance from the perspectives of bathing, dressing, grooming, initiation, toileting and feeding, with six items and a sum of scores ranging from 0 (normal) to 24 (complete dependence on others). And modified Lawton Instrumental Activities of Daily Living Scale will be used to measure the IADL of a subject, with eight items and a sum of scores ranging from 0 (normal) to 32 (complete dependence on others).

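### Section 4.2 tests the 11 ADAS-cog items and seven secondary scores under the primary outcome's unadjusted one-sided 0.05 rule: 18 extra tests at one time point, with multiplicity controlled only for microbial taxa

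*Combined protocol and SAP*

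**What the plan says.** Section 3.3.1 names ADAS-cog as the primary outcome. Section 3.3.2 lists the rest: "Secondary measures includes the MMSE, MoCA (Changsha Version), CDR, PSQI, ADLs, and gut microbiome". CDR yields two scores, because "The CDR sum of boxes (CDR-SB) scored 0-18, will also be applied" alongside the global rating, and ADLs yield two, BADL and IADL.

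Section 4.2 gives one analysis for all the clinical outcomes: "ADAS-cog (including its monomial item) changes from baseline and the secondary outcomes will be assessed using an analysis of covariance", with treatment group as factor and baseline value as covariate. One decision rule follows: "The statistical significance is defined as a one-sided P-value of <0.05 and 95% confidence interval". It does not distinguish the primary total from the single items or the secondary scores. No testing order, split of alpha or exploratory label is given for these outcomes.

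The section does adjust for multiplicity elsewhere. For the microbiome, a Benjamini-Hochberg adjustment "will be used to account for the number of taxa tested in each comparison".

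Section 1 sets sleep as the second aim: "the investigators intend to assess whether YZASG can improve sleep quality among aMCI patients". PSQI, the measure for that aim, is one entry in the list of secondary measures, with no designated visit.

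**The concern.** The same rule that decides the primary comparison can be applied, without adjustment, to each ADAS-cog item and each secondary score. Suppose the ADAS-cog total shows no difference. The plan as written still allows a favourable single item, or a favourable MMSE, MoCA or ADL result, to be declared statistically significant. A reader could take that as evidence of cognitive or functional benefit when it is a chance finding from a set of many tests.

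The items deserve most attention. They are components of the primary scale, so a significant item can easily be presented as partial support for the primary hypothesis. The sleep objective is also exposed: it is a stated aim, but its measure has no status separating it from the other secondary scores and no visit fixed in advance.

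**Working it through.** The plan gives no number of tests and no family-wise error rate, so there is no figure of its own to reproduce.

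**Inputs**
- ADAS-cog items: 11, read from the subscript in the scale's name in section 3.3.1. The items are not listed, and the wording about a monomial item in section 4.2 is taken to mean each single item.
- Secondary clinical scores (section 3.3.2): MMSE, MoCA, CDR global, CDR-SB, PSQI, BADL and IADL, which is 7. The microbiome has its own adjustment and is left out.
- Error per test: 0.05, one-sided (section 4.2).
- Correlation between tests: not documented. Values of 0.3 and 0.5 are assumed, with 0.7 as a higher case.

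**One time point**
- Tests beyond the ADAS-cog total: 11 + 7 = 18.
- Expected false positives with no treatment effect: 18 × 0.05 = 0.9, whatever the correlation.
- Chance of at least one, independent tests: 1 − 0.95^18 = 0.603.
- With correlated tests, modelled as normal statistics with a common correlation: 0.42 at 0.3, 0.32 at 0.5 and 0.23 at 0.7.
- The seven secondary scores alone: 7 × 0.05 = 0.35 expected; chance of at least one 1 − 0.95^7 = 0.30 if independent, 0.20 at correlation 0.5.

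**If the interval in the rule is binding**

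The rule pairs a one-sided P below 0.05 with a 95% confidence interval. If that interval is two-sided and must exclude zero, the error per test in the favourable direction is 0.05 / 2 = 0.025.
- Expected: 18 × 0.025 = 0.45.
- Chance of at least one: 1 − 0.975^18 = 0.366 if independent; about 0.26 and 0.20 at correlations 0.3 and 0.5.

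**If every post-baseline visit is tested**

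This is a conditional case. ADAS-cog has four post-baseline visits, "at 16 weeks (the end of intervention) and 6, 12, and 18 months after intervention". Section 3.3.2 schedules the questionnaires at five: weeks 8 and 16, and three follow-up visits.
- Tests: 11 × 4 + 7 × 5 = 44 + 35 = 79.
- Expected: 79 × 0.05 = 3.95, or 79 × 0.025 = 1.98 on the stricter reading.
- Chance of at least one at 0.05: 1 − 0.95^79 = 0.98 if independent; about 0.72, 0.53 and 0.36 at common correlations of 0.3, 0.5 and 0.7.

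| Reading | Tests | Expected at 0.05 | Expected at 0.025 |
|---|---|---|---|
| One time point | 18 | 0.9 | 0.45 |
| Every post-baseline visit | 79 | 3.95 | 1.98 |

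**The case against.** The strongest reply is that the plan does have a hierarchy. Section 1 ranks the objectives, section 3.3.1 names one primary outcome with one hypothesis, and section 3.3.2 labels the rest secondary. A significant item after a null total would not count as success on the primary outcome. Leaving secondary outcomes unadjusted and treating them as supportive is common in a trial of 80 participants. This stands in part: it would be wrong to say that the plan has no order at all. But the hierarchy never reaches the decision rule. Section 4.2 neither makes secondary or item claims depend on the primary nor calls them exploratory.

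A second reply concerns the count. A reader might infer that 79 tests and about four false positives are what the plan commits to. The documents do not support that. Section 3.3 says when the scales are administered; section 4.2 does not say that each visit is tested, and the primary hypothesis is a single contrast from baseline to an unspecified endpoint. Nor is 79 a ceiling. Adding the ADAS-cog total at four visits gives 79 + 4 = 83, and repeating the 79 in the full analysis and per-protocol sets gives 158. The single-time-point figure of 18 is the safer basis.

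A third reply is that the interval in the significance rule may halve the error per test. The sentence is ambiguous, since a one-sided 95% bound would match 0.05. Both readings are therefore shown.

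A reader might also infer that a negative PSQI result becomes uninterpretable. It does not. Unadjusted testing makes false positives easier, and a PSQI test at one named visit keeps its nominal error. The sleep problem is the missing visit and the missing status.

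**Conclusion.** The concern holds for the item and secondary claims. At one time point the plan permits 18 unadjusted tests beyond the primary total. With no treatment effect, 0.45 to 0.9 false positives are expected, depending on how the significance rule is read. The chance of at least one is 20% to 60% over correlations from 0 to 0.5, and lower if the scores are more strongly correlated. The expected counts do not depend on correlation; the chances do, and the correlations are assumed. The count also rests on reading 11 items from the scale's name.

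The all-visits case is a scenario only. Correlation between visits, which last observation carried forward would tend to raise, makes false positives cluster without changing their expected number.

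A claim on the ADAS-cog total at one prespecified visit would not be affected by the item and secondary tests. The change should be made because the other claims, including the sleep claim, cannot be read reliably under the present rule.

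**What to change.** Add two or three sentences to section 4.2:

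1. Only the ADAS-cog total, at one visit that the sponsor names in advance, is confirmatory.
2. PSQI at one named visit is the single key secondary test, for the sleep objective. Testing it in fixed sequence after the primary is optional. With the sequence, the chance of any false claim across the two stays at 5%, but there is no confirmatory sleep test if the primary fails. Without it, the chance is at most 0.05 + 0.05 = 10%.
3. The ADAS-cog items and all other scores and visits are reported as adjusted differences with 95% confidence intervals and are not called significant. Alternatively, they are adjusted by Benjamini-Hochberg, as the taxa are, with the family and level stated. That method controls the false discovery rate. If no outcome in the family has an effect, this equals the chance of any false positive, so the method still limits it in the null case considered here, for independent or positively dependent tests.

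The same edit should say whether the 95% interval in the significance rule is one-sided or two-sided and whether it must exclude zero.

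Sample size, visits and data collection do not change. The downside is that fewer item and secondary results can be called significant.
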